## **Intervention**

In the PEB arm, the intervention will include:

A charge nurse will intervene in real-time via an EHR-triggered alert when there is documentation that a dose of VTE prophylaxis medication is not given for any reason. The charge nurse will speak to the bedside nurse and one of them will provide the patient with the education bundle including one-on-one personalized discussion, supplemented by a 2-page paper handout and patient education video.

In the NFC arm, the intervention will include:

Nurse leadership (i.e. managers, directors) will provide data to all nurses on their personal clinical effectiveness with the proportion of doses of VTE prophylaxis administered. The data will have comparisons to their nurse peers on the same floor. Coaching for nurses will include one-on-one conversations with bedside nurses with lower performance than their peers.

## **Primary Outcome:**

Missed doses of VTE prophylaxis

## **Secondary outcomes:**

Patient refused doses of VTE prophylaxis

Missed doses of VTE prophylaxis for reasons other than patient refusal

VTE events (all VTE, DVT, PE)

Patient satisfaction (via surveys and HCAHPS scores)

## Nurse satisfaction

### **Analysis plan**

We will have a blinded biostatistician team perform all analyses.

We will use the intention-to-treat (ITT) approach.

We will compare outcomes across intervention periods.

We will compare outcomes based upon randomized floor.

We will use multiple outputation to reduce the levels of hierarchical structure to the floor and nurse level by randomly selecting one VTE prophylaxis dose per patient and reiterate the procedure 1000 times to bootstrap the p values for the comparisons. This methodology will be similar that taken previously in our prior work in similar circumstances.

We will adjust by floor type (medicine vs. surgery) and patient level characteristics (race, sex, age, insurance) when calculating proportions and risk of missed doses.

We will conduct a sensitivity analysis (excluding floors where prior intervention occurred).

Check for differential effect that may eliminate biases in pre-implementation data (by race, age, sex)

PRE-TRIAL (6 MONTHS)	PERIOD I (3 MONTHS)	PERIOD II (3 MONTHS)	POST-TRIAL (3 MONTHS)	
RANDOMIZATION	<pre> graph LR     A[RANDOMIZATION] --> B[PEB]     A --> C[NFC]     B --> D[NFC+PEB]     B --> E[PEB+NFC]     C --> D     C --> E     D --> F[POST-TRIAL PERIOD]     E --> F   </pre>	<pre> graph LR     A[RANDOMIZATION] --> B[PEB]     A --> C[NFC]     B --> D[NFC+PEB]     B --> E[PEB+NFC]     C --> D     C --> E     D --> F[POST-TRIAL PERIOD]     E --> F   </pre>	POST-TRIAL PERIOD	
Randomization with sequence generator	Block (Medicine): 5 Medicine floors- PEB 5 Medicine floors- NFC  Block (Surgery): 3 Surgery floors- PEB 3 Surgery floors- NFC	Block (Medicine): 5 Medicine floors- PEB+NFC 5 Medicine floors- NFC+PEB  Block (Surgery): 3 Surgery floors- PEB+NFC 3 Surgery floors- NFC+PEB	Observation assessment

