**Primary hypothesis**

Both interventions (PEB and NFC) will improve medication administration (as measured by missed doses)

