## **Participants**

### **Eligibility Criteria**

Participating floors will be assigned one of two interventions based on a randomization sequence.

Eligible floors are defined as:

- A. All medical and surgical floors (non- intensive care units)
- B. 16 total floors (10 medicine, 6 surgery)

Eligible Patients are defined as: All patients on assigned floors except:

- A. Patient data for those transferred between floors will be excluded.
- B. Patient data for those on floors during the cross-over time will be excluded.

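### The plan keeps floor and nurse levels but does not provide for floor-by-period variation; with model-based standard errors, across-period tests of missed doses would be anti-conservative if floors drift differently

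*Combined protocol and SAP*

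**What the plan says.** On clustering, the Analysis plan says that multiple outputation will "reduce the levels of hierarchical structure to the floor and nurse level by randomly selecting one VTE prophylaxis dose per patient", and that the team will "reiterate the procedure 1000 times to bootstrap the p values for the comparisons". On contrasts it says "We will compare outcomes across intervention periods" and "We will compare outcomes based upon randomized floor".

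The design table follows 16 floors (10 medicine, 6 surgery) through a 6-month pre-trial phase, two 3-month trial periods and a 3-month post-trial phase. In Period I, 8 floors have PEB and 8 have NFC (5 and 5 medicine, 3 and 3 surgery). In Period II all 16 floors have both.

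The primary hypothesis is: "Both interventions (PEB and NFC) will improve medication administration (as measured by missed doses". Secondary hypotheses 1 and 2 say that the combination lowers refused doses and doses missed for other reasons.

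The plan names no floor-by-period or nurse-by-period effect and no correlation between a floor's periods. It also names no regression model, variance estimator, resampling unit for floors, small-sample correction or alpha.

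**The concern.** No floor is untreated at any time during the trial: both arms are active in Period I, and every floor has both interventions in Period II. A claim that both interventions improve administration, or that the combination lowers missed doses, therefore rests on the same floors compared with themselves at another time.

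In that contrast a floor's stable level drops out, and so, largely, does the level of a nurse who works in both periods. What remains is patient-level sampling noise plus any change particular to that floor in that period, for example from staffing, case mix or leadership. An analysis with only floor and nurse effects counts the first and leaves out the second. Outputation does not help. Drawing one dose per patient removes the correlation among doses within a patient, and repeating the draw 1000 times leaves floor-by-period variance as it was.

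At stake is whether ordinary quarter-to-quarter movement on 16 floors could be declared a significant improvement on the primary hypothesis.

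**Working it through.** The documents state no type I error, power, sample size or intraclass correlation, so there is no planned figure to reproduce. The floor count agrees with itself: 5+5+3+3 = 10+6 = 16.

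**Inputs from the documents.** Missed-dose proportion p = 0.12 (Background), so p(1-p) = 0.12 x 0.88 = 0.1056. There are 16 floors, 8 per arm. The pre-trial phase lasts two quarters and Period I one quarter.

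**Assumed inputs.** Two-sided alpha 5%; m = 150 to 400 patients per floor-quarter, one dose each after outputation; floor-by-period SD tau = 1 to 3 percentage points per quarter, independent between quarters.

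**Variance of one floor's change** (Period I minus the mean of two pre-trial quarters):
- True: (1 + 1/2) x tau^2 + (1 + 1/2) x p(1-p)/m
- With floor and nurse effects only: (1 + 1/2) x p(1-p)/m
- Ratio: R = 1 + m x tau^2 / 0.1056. The factor 1 + 1/2 cancels, so R is the same for two single quarters.

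**Actual type I error** = 2 x [1 - Phi(1.96/sqrt(R))].

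| m | tau (points) | R | Type I error |
|---|---|---|---|
| any | 0 | 1.00 | 5.0% |
| 50 | 1 | 1.05 | about 5.6% |
| 150 | 1 | 1.14 | 6.7% |
| 250 | 1 | 1.24 | 7.8% |
| 250 | 1.5 | 1.53 | 11% |
| 250 | 2 | 1.95 | 16% |
| 250 | 3 | 3.13 | 27% |
| 400 | 3 | 4.41 | 35% |

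Example: m = 250, tau = 0.02 gives R = 1 + 250 x 0.0004/0.1056 = 1.95, and 1.96/sqrt(1.95) = 1.40, a two-sided tail of 16%.

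**Does the nurse level absorb the drift?** Simulation with nurses who work in every period (m = 250, 16 floors, assumed floor SD 4 points and nurse SD 3 points) gave 5.3%, 8.1%, 15.9% and 27.5% rejections at drift SD 0, 1, 2 and 3 points. With 8 floors it gave 5.1%, 7.7%, 15.8% and 26.8%. These match the formula, so it does not. Nurse turnover was not simulated. A paired test on floor-level changes held 4.7-5.6% in the same runs.

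**Second parametrisation.** With within-period ICC rho and between-period correlation c of a floor's effects, R = 1 + m x rho x (1-c)/(1-rho). For m = 200, rho = 0.02, c = 0.8: R = 1 + 200 x 0.02 x 0.2/0.98 = 1.82, or 14.6% (simulated 14.8%). With c = 1 it is 5%. Over a wide assumed grid (m 50-400, rho 0.005-0.10, c 0.5-1) the range is 5.0% to 68%.

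**Analyses that behave differently** (16 floors, 20,000 runs per scenario):
- Paired t-test on 16 floor-level changes, 15 df: 4.8-5.3%.
- z-test with variance clustered on floors, uncorrected: about 7.5-8.1% whatever the drift. This excess comes from having 16 clusters, not from drift.
- PEB versus NFC in Period I alone, 8 versus 8 floor means: 4.8-5.3%.

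**The case against.** The strongest reply is that the plan leaves its model unstated rather than choosing a wrong one. The sentence on outputation describes what is stripped out, namely repeated doses within a patient. Floor and nurse are the levels that remain, which is not the same as a list of random intercepts. Variance clustered on whole floors, or resampling of whole floors, would also fit that sentence and would cover floor-by-period drift. The plan further refers to the team's earlier methodology, which is not reproduced. All of this stands, and it is why the point is conditional on model-based standard errors. It does not remove the point. The only resampling described draws doses within patients, and nothing in the text leads an analyst to an approach that covers the drift.

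The size is also open to challenge. Patients per floor, drift and alpha are all assumed, and with small floors and little drift the inflation is trivial. That stands too.

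A reader might infer more than the documents support:
- *Every across-period standard error is too small.* This needs both non-zero drift and model-based standard errors, and the documents establish neither.
- *The randomized comparison of PEB with NFC is also invalid.* Within Period I there is no change over time to estimate, so this mechanism does not act. It would enter if pre-trial data were added to that model, but the plan describes no such model.
- *The same figures apply to VTE events (hypothesis 8) or to the effect-modifier hypotheses 5 and 7.* The calculations use the 12% missed-dose rate. The documents give no VTE rate, and nothing was computed for effect modifiers.

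**Conclusion.** The concern holds in conditional form. The plan compares the same 16 floors over time, its primary hypothesis depends on that comparison, and it provides for no floor-by-period variation. Under floor and nurse effects with model-based standard errors, tests of the primary hypothesis and of secondary hypotheses 1 and 2 would reject too often whenever floors drift differently between periods.

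The 7-35% range is an illustration that depends on the assumed alpha, patient counts and drift; it is not a property of the trial that the documents establish. What is certain from the documents is the omission and the direction of the error, given drift and that variance method. Because the primary claim has no concurrent untreated comparison to fall back on, this should be settled before analysis rather than left to the analyst.

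**What to change.** Add one sentence to the Analysis plan that adopts one of these:

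1. Every model that uses more than one period includes a floor-by-period random effect, with tests referred to a small-sample distribution based on the number of floors.
2. Within each outputation draw, reduce the data to one change per floor and test the 16 changes on 15 df (8 floors, 7 df, for a change within one arm).
3. Use variance clustered on whole floors with a small-sample correction. Without the correction, 16 floors gave about 7.5-8.1% in simulation.

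State alpha in the same place. No new data are needed. The cost is wider confidence intervals for the across-period results, more so for a single arm with 8 floors. The PEB-versus-NFC comparison within Period I needs no change on this account.

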**Secondary hypotheses**

1. Combining both interventions (PEB and NFC) will decrease patient refusal of VTE prophylaxis
2. Combining both interventions (PEB and NFC) will decrease missed doses for reasons other than patient refusal

3. Overall, PEB intervention will be more effective than NFC in reducing missed doses for any reason:
  - a. The PEB intervention will be more effective than NFC in reducing in reducing patient refusal
  - b. The NFC intervention will be more effective than PEB in reducing missed doses for other reasons of missed doses other than patient refusal
4. There will be a differential effect on medicine and surgery floors
5. There will be a differential effect by patient level characteristics (race, age, sex)
6. There will be a differential effect on high vs. low performing floors
7. There will be a differential effect dependent on pharmacological dosing regimen (i.e. medication, frequency)
8. There will be an overall decline in the incidence of VTE events (all, DVT, PE)

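### The only stated p-value rule (bootstrapping p-values from 1000 one-dose redraws) does not match the multiple outputation the plan names, and no combination rule or 16-floor reference is given

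*Combined protocol and SAP*

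**What the plan says.** The Analysis plan section says that multiple outputation will be used to "reduce the levels of hierarchical structure to the floor and nurse level". The method is "randomly selecting one VTE prophylaxis dose per patient and reiterate the procedure 1000 times to bootstrap the p values for the comparisons". The only pointer to further detail is this sentence: "This methodology will be similar that taken previously in our prior work in similar circumstances". The same section says "We will compare outcomes based upon randomized floor" and "We will compare outcomes across intervention periods". It lists the adjustment variables: floor type, race, sex, age and insurance.

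Neither that section nor any other section available for review gives a per-draw model or standard error, a formula for combining the 1000 draws, a way of handling the floor and nurse clustering that remains, degrees of freedom, a permutation test or an alpha level. Eligibility Criteria fixes the number of clusters at 16 floors, and the design table allocates 5 v 5 medicine and 3 v 3 surgery floors. The primary hypothesis, "Both interventions (PEB and NFC) will improve medication administration (as measured by missed doses", names no comparator.

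**The concern.** Multiple outputation is a sound choice here. It discards within-patient correlation at each draw and recovers the lost information by averaging. Its inference comes from the estimates and their variances. The stated rule attaches the repetition to the p-values instead.

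Redrawing doses within a fixed set of patients varies nothing except the dose picked. Patients, nurses and floors stay the same in every redraw, although floors are the randomized unit. The spread of the redraws is the component that outputation subtracts, so it cannot serve as the error term. The plan itself does not treat floors as alike. One secondary hypothesis reads "There will be a differential effect on high vs. low performing floors", and a sensitivity analysis is planned "excluding floors where prior intervention occurred".

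The sentence can be carried out in several ways, and their errors run in opposite directions. A p-value from the redraw spread can turn ordinary variation between floors into an effect. Averaging valid floor-level p-values can hide a real effect. Correct combination with a large-sample reference is mildly to moderately liberal with 16 floors. The choice affects every comparison in the plan.

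**Working it through.** The plan states no sample size, power or alpha, so it has no figure to reproduce.

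**Inputs from the document.** About 12% of doses missed (Background); 16 floors in 5/5 and 3/3 blocks; 6-month pre-trial period and 3-month Period I; 1000 draws.

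**Assumed inputs.** Two-sided 5%; n = 200 or 500 patients per floor per 3 months; geometric number of doses per patient, mean 10; within-patient correlation ρ = 0.5 or 0.25; between-floor CV of the missed-dose rate 0, 0.1, 0.2 or 0.3 (for CV above 0, ICC = CV² × 0.12/0.88 = 0.0014, 0.0055, 0.012). No nurse level or patient covariates.

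**Outputation rule.** Draw k gives estimate b_k with variance v_k. By the law of total variance, the mean of the b_k has variance mean(v_k) − between-draw variance of the b_k.

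**Redraw spread used as the error term, PEB v NFC.** Take p(1−p)/n as the unit of variance for a floor mean. A one-dose draw then splits into w + v = 1. Here v = ρ + (1−ρ)E(1/m) is the variance of patient means, w = (1−ρ)(1 − E(1/m)) is the dose-selection part, and m is the number of doses. With mean 10, E(1/m) = 0.1 × ln(10)/0.9 = 0.256.
- ρ = 0.5: v = 0.628, w = 0.372.
- ρ = 0.25: v = 0.442, w = 0.558.

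Floors add n·CV² × 0.12/0.88 = 0.1364·n·CV². The error rate is 2(1 − Φ(1.96·√(w/(v + 0.1364·n·CV²)))). For example, with n = 200, ρ = 0.25 and CV 0.2, 0.1364 × 200 × 0.04 = 1.091, √(0.558/1.533) = 0.603, 1.96 × 0.603 = 1.18, and the error is 0.237.

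| n | ρ | CV 0 | CV 0.1 | CV 0.2 | CV 0.3 |
|---|---|---|---|---|---|
| 200 | 0.5 | 0.131 | 0.208 | 0.362 | 0.496 |
| 200 | 0.25 | 0.028 | 0.083 | 0.237 | 0.390 |
| 500 | 0.5 | 0.131 | 0.296 | 0.514 | 0.646 |
| 500 | 0.25 | 0.028 | 0.167 | 0.411 | 0.568 |

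Simulation (4,000 null trials per cell) agrees within 0.01. At ρ = 0.25 the error passes 5% when 0.1364·n·CV² exceeds 0.558 − 0.442 = 0.116, that is, at CV 0.065 (n = 200) or 0.041 (n = 500).

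**Other readings, same contrast.**
- Mean of 1000 floor-level p-values: 0.00-0.04.
- Outputation rule, floor-level residual variance, t with 13 df: 0.045-0.054.
- Outputation rule, t with 13 df, cluster sandwich (including floors of unequal size): uncorrected 0.07-0.19; with a G/(G−1) factor 0.06-0.14; bias-reduced (CR2) 0.045-0.062.
- Permutation of the averaged estimate: 0.044-0.053. There are 252 × 20 = 5,040 blocked allocations, so the smallest two-sided p is about 2/5,040 = 0.0004.

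A second simulation used 100 patients per floor, mean 8 doses, ICC 0/0.01/0.03 and correlation 0.3 or 0.7. The pattern was the same: redraw tail area 1.2-61%, mean floor-level p-value 0-3.1%, outputation rule with t(13) 4.3-5.8%. With a normal reference the rule gave 6.2-8.0% (theory 7.2%; critical values 2.160 and 1.960). Leaving out the floor term is unsafe even when draws are combined correctly (20-49% at ICC 0.01-0.03) or p-values are averaged (up to 27%).

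**Comparison across periods, taking pre-trial v Period I as an example.** Stable floor differences cancel within floors. With no floor-by-period variance, the simulated redraw spread gives 0.12-0.14 at ρ = 0.5 and 0.02-0.03 at ρ = 0.25. With a floor-by-period CV of 0.1/0.2/0.3 it gives 0.06-0.25, 0.17-0.45 and 0.30-0.59. The outputation rule with a paired floor-level variance gives 0.044-0.061.

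**Power, PEB v NFC, assumed risk ratio 0.75, n = 200, ρ = 0.25, CV 0/0.1/0.2/0.3.** Averaged p-values 60/48/33/22%; outputation rule with floor-level variance 97/88/58/36%.

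**The case against.** The sentence names multiple outputation, a recognized procedure, so the bootstrap clause may be loose shorthand for it. The plan keeps floor and nurse as levels and says that outcomes will be compared by randomized floor, and the combination rule may be set out in the prior work it mentions. The redraw-spread reading gives floors and nurses no role, so it fits the rest of the text least well, yet it produces the largest error figures. Correlation, patients per floor and floor variance are all assumed, and one set of assumptions shows no inflation.

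Much of this stands. A reader might infer that the plan ignores clustering, or that its p-values will be wrong by up to the largest figure above. The document supports neither: it retains the floor and nurse levels, and it does not show which computation will be run. A reader might also take the primary hypothesis to be a test of change from the pre-trial period, but the document states no such contrast.

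Two things remain. The only rule written down is not the named method's rule, and the prior work is neither cited nor reproduced. Even if standard outputation is intended, 16 floors need a small-sample method and none is named.

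**Conclusion.** The point holds as a mismatch and an omission: the p-value rule as worded is not valid outputation inference, and the plan gives nothing in its place. The size is conditional on the assumed inputs. For PEB v NFC in Period I, the possible readings run from about 0.00 to 0.65 at a nominal 5%, while a correctly specified rule holds about 0.05. If the team intends the standard rule, the remaining problem is the small-sample reference, worth about 0.06-0.08 with a normal reference or 0.07-0.19 with an uncorrected sandwich. For comparisons across periods, inflation depends on patient heterogeneity and floor-by-period variation, and the document gives no size for either.

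The near-5% rates come from a model without the nurse level or covariates, so they support the principle of the fix and do not test the full adjusted analysis. This should be fixed before analysis; it does not show that the trial's results will be wrong.

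**What to change.** Delete the clause about bootstrapping p-values and state the following.

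- **Combination.** The effect is the mean of the 1000 adjusted estimates. Its variance is the mean within-draw variance minus the between-draw variance. Say what is done if that difference is not positive.
- **Within-draw variance.** Cluster at the floor, the randomized unit, which also covers nurses who work within one floor. Use the floor-level residual variance or CR2, not an uncorrected sandwich.
- **PEB v NFC in Period I.** Use t with about 13 df (16 floors minus intercept, arm and floor type), or a permutation test of the averaged estimate over the 5,040 blocked allocations.
- **Comparisons across periods.** Use paired floor-level changes with df matched to the floors in the contrast: 7 for one arm of 8 floors, 15 if all 16 are pooled, one fewer if floor type is in the model. State which contrast tests the primary hypothesis.
- **Prior work.** If it already uses this rule, cite it and write the rule into the plan.

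The cost is plan text and code, with no new data. Intervals will usually be wider than the redraw spread would give: the critical value is 2.16 at 13 df and 2.36 at 7 df, against 1.96. In the assumed scenario with risk ratio 0.75, n = 200, ρ = 0.25 and CV 0.2, rejections fall from 86% with the redraw spread, which is not a valid test there, to 58%.

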**Background**

Missed doses of prescribed Venous Thromboembolism (VTE) pharmacologic prophylaxis is significant problem. Data on patients admitted to The Johns Hopkins Hospital found approximately 12% of prescribed doses of pharmacologic VTE prophylaxis were not administered. There were several reasons for these missed doses. The leading reason (nearly 60% of missed doses) was patient or family member refusal for any reason.

Based on data collected by the Maryland Health Services Cost Review Commission (HSCRC) in the Maryland hospital-acquired conditions (MHAC) program, during 2011 half of patients who developed confirmed VTE at The Johns Hopkins Hospital were not administered one or more doses of prescribed VTE prophylaxis. These data indicate that missed or refused doses of VTE prophylaxis represent a significant and under-recognized contributor to sub-optimal VTE prophylaxis that will erode the beneficial impact of current efforts to improve rates of VTE prophylaxis ordering by physicians.

As part of a Patient-Centered Outcomes Research Institute (PCORI)-funded project, the investigators have developed a registry of missed doses of VTE prophylaxis that includes data on missed doses of VTE prophylaxis.

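### Pre-specifying each floor's pre-trial missed-dose rate as a covariate would probably sharpen the Period I PEB-versus-NFC comparison at little cost

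*Combined protocol and SAP*

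**What the plan says.** Eligibility Criteria gives the number of clusters: "16 total floors (10 medicine, 6 surgery". In the schedule table of the Analysis plan, Period I splits the ten medicine floors 5 to 5, and the surgery block reads "3 Surgery floors- PEB 3 Surgery floors- NFC". In Period II every floor has both interventions; the medicine block, for example, reads "5 Medicine floors- PEB+NFC 5 Medicine floors- NFC+PEB".

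For adjustment, the Analysis plan says: "We will adjust by floor type (medicine vs. surgery) and patient level characteristics (race, sex, age, insurance". No floor-level measure of past performance is on that list.

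Two places suggest that such a measure could be had. The schedule table opens with "PRE-TRIAL (6 MONTHS", and Background says that "the investigators have developed a registry of missed doses of VTE prophylaxis that includes data on missed doses of VTE prophylaxis".

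Three other statements bear on the point:

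- The Analysis plan says "We will compare outcomes across intervention periods", without naming a model or a baseline term.
- Secondary hypothesis 6 expects the effect to differ between better- and worse-performing floors. It does not define performance, and it treats it as an effect modifier, not as an adjustment covariate.
- The Analysis plan says "We will conduct a sensitivity analysis (excluding floors where prior intervention occurred", without giving the number of floors excluded.

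**The concern.** The comparison of PEB with NFC (secondary hypothesis 3, with 3a and 3b by reason for the missed dose) has only 16 clusters to work with, and the floors named as eligible cannot be increased. In such a design the spread between floors largely sets the width of the confidence interval. A floor's own past missed-dose rate is a natural predictor of its rate in Period I. Leaving it out may give a less precise answer than data the trial probably already holds would allow. Adding it only after outcomes are known would be less credible, because with 16 floors the choice of one covariate can move the estimate noticeably.

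**Working it through.** **Inputs from the documents.** 16 floors in two blocks; Period I allocation 5 + 3 = 8 PEB floors and 5 + 3 = 8 NFC floors; about 12% of doses missed (Background). The plan gives no power calculation, alpha, between-floor SD, volume per floor or correlation over time, so it has no figure of its own to reproduce.

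**Assumed.** Two-sided 95% intervals; a linear model on floor-level rates; r, the correlation between observed pre-trial and Period I floor rates net of floor type and patient covariates, shown over a range.

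**Step 1: against a model with no pre-trial data.** A floor-level model with intercept, arm and floor type leaves 16 − 3 = 13 degrees of freedom (t = 2.160). Adding the pre-trial rate leaves 12 (t = 2.179). Estimating the slope multiplies the variance by 1 + 1/11 = 12/11, and the covariate removes the share r².

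Half-width ratio = √(1 − r²) × √(12/11) × 2.179/2.160 = 1.053 × √(1 − r²)

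| r | ratio | 95% CI |
|---|---|---|
| 0 | 1.053 | 5% wider |
| 0.3 | 1.005 | about unchanged |
| 0.5 | 0.912 | 9% narrower |
| 0.6 | 0.843 | 16% narrower |
| 0.7 | 0.752 | 25% narrower |

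Break-even: r² = 1 − 1/1.053² ≈ 0.099, so r ≈ 0.31.

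**Step 2: how high r can be.** Take an assumed 600 pre-trial and 300 Period I observations per floor, 12% missed doses and a true floor SD of 3 points (variance 0.0009).

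- Sampling variances: 0.12 × 0.88/600 = 0.000176 and 0.12 × 0.88/300 = 0.000352.
- Reliabilities: 0.0009/0.001076 = 0.84 and 0.0009/0.001252 = 0.72.
- Ceiling on r: √(0.84 × 0.72) ≈ 0.78, even if the true floor rates were perfectly stable.

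True correlations of 0.7 and 0.9 then give observed r of about 0.54 and 0.70, so intervals about 12% and 25% narrower. A simulation with binomial counts agreed closely: the mean half-width fell from 3.7 to 3.2 points and from 3.7 to 2.7 points. Type I error stayed between 4.4% and 5.5% with and without the covariate.

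**Step 3: patient covariates already in the plan.** If the correlation before patient adjustment were 0.7 and case mix explained a quarter of the variance shared by the two windows (both assumed), net r would be 0.636 with a pre-trial rate adjusted for the same patient characteristics, or 0.578 with a raw one. The gain falls from 25% to 19% or 14%. If case mix explained half, it falls to 11% or 5%.

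**Step 4: against a change-from-baseline analysis.** With equal variances in both windows, a change score has variance proportional to 2(1 − r). The half-width ratio of covariate adjustment to change score is then 1.053 × √((1 + r)/2): 0.91 at r = 0.5, 0.97 at 0.7 and 1.00 at 0.8. The gain is about 9%, 3% and nil.

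**Step 5: fewer floors.** With N floors, the cost at r = 0 is √((N − 4)/(N − 5)) × t(0.975, N − 4)/t(0.975, N − 3) = 1.067, 1.090 and 1.134 for an assumed N = 14, 12 and 10. Break-even r rises to 0.35, 0.40 and 0.47.

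**The case against.** The strongest reply is that nothing is broken. Randomisation makes the planned PEB-versus-NFC estimate unbiased, the comparison is secondary, and baseline adjustment is optional. That stands, and it sets the grade of this point.

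The second reply is that the gain is unproven, because the documents give no correlation, between-floor SD or volume. This also stands. The result is a range, with a small loss at its lower end.

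The third is that comparing outcomes across periods, with a pre-trial period in the schedule, may already bring the baseline in. It may. The sentence names no model, so neither reading can be excluded, and under a change-from-baseline reading most of the gain at higher r disappears. At r = 0.5 or below, covariate adjustment would still be more precise than a change score.

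The fourth is that secondary hypothesis 6 already brings in floor performance. It does so only as an undefined effect modifier, which does not adjust the comparison of PEB with NFC.

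The last is that the planned analysis uses multiple outputation on single doses, keeping floor and nurse levels, and not a 16-floor linear model. The covariate is constant within a floor and can enter every outputation fit, but the gain in that analysis was not calculated and may differ somewhat.

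**Conclusion.** The point holds as a low-cost improvement worth considering, with medium confidence. The omission from the adjustment list is clear, and the worst-case cost with 16 floors is an interval about 5% wider. The likely benefit is a modest to moderate narrowing: about 9% to 25% for r between 0.5 and 0.7 if the planned model uses no pre-trial data, and about 9% to 3% over the same range if it is a change-from-baseline analysis. All of this rests on an assumed r and a floor-level linear model.

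A reader might infer more, in three ways that the documents do not support:

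- **That the planned comparison is biased or wrong.** Floors are randomised within medicine and surgery blocks, so only precision is at issue.
- **That intervals could be 40% or 50% narrower.** This would need r well above 0.7, which sampling noise may put out of reach.
- **That the primary hypothesis is affected.** It says that both interventions improve administration and appears to rest on comparison across periods, where this covariate has no part.

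**What to change.** Add to the Analysis plan that the Period I PEB-versus-NFC model includes each floor's missed-dose rate over the six pre-trial months as a floor-level covariate, with reason-specific rates for hypotheses 3a and 3b where available. Fix this before outcome data are seen. Report the result without the covariate as a sensitivity analysis, and state that the covariate is not used in the before-after comparison for the primary hypothesis. The same text should say what comparing across intervention periods means for this contrast, so that the baseline is not used twice.

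The cost is a sentence or two, one floor-level degree of freedom, and extraction of the pre-trial floor rates. The documents imply that these rates are obtainable but do not say that they are tabulated by floor. A pre-trial rate adjusted for the same patient characteristics would gain a little more, but it needs a separate patient-level model of the pre-trial window.

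The statistical downside is an interval up to about 5% wider if r is below about 0.3. In the sensitivity analysis that drops floors with a prior intervention, it would be 7% to 13% wider at r = 0 if 14 to 10 floors remained (numbers assumed).
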